5.3.5 Supplementary Analyses for Primary Endpoints

The following supplementary analyses will be performed for the co-primary efficacy endpoints of PFS and OS in which a different handling rule of intercurrent events is implemented to provide further understanding of the treatment effect.

5.3.5.1 Subgroup Analyses for Primary Endpoints

The generalizability of OS and PFS results when comparing the Tira+ACE arm to the Pbo+ACE arm will be investigated by estimating the treatment effect in subgroups defined by demographics (e.g., age, sex) and baseline prognostic characteristics (e.g.,

ECOG Performance Status, LDH). Summaries of OS and PFS, including unstratified HRs estimated from Cox proportional hazards models and Kaplan-Meier estimates of median PFS and OS will be provided separately for each level of the subgroups for the comparisons between treatment arms.

5.4 SECONDARY ENDPOINTS ANALYSES

5.4.1 Key Secondary Endpoints

5.4.1.1 Progression-Free Survival and Overall Survival in the Full Analysis Set

The estimand is defined similarly as for the co-primary endpoints of PFS and OS in Section 5.3.1 with the exception of the following:

Population: Patients with previously untreated extensive-stage small cell lung cancer.

Same analytical approaches for primary analysis of PFS and OS specified in Section 5.3 will be used to analyze PFS and OS on the FAS.

Subgroup analyses of PFS and OS on the FAS will also be provided by the baseline prognostic factor of presence or history of brain metastases.

5.4.1.2 Confirmed Overall Response Rate

The estimand for confirmed overall response rate (ORR) is defined as follows:

- Population: Patients with previously untreated extensive-stage small cell lung cancer without presence or history of brain metastases at baseline
- Variable: Whether patients achieved a confirmed objective response (i.e., complete response [CR] or partial response [PR] on two consecutive occasions ≥ 4 weeks apart), as determined by the investigator according to RECIST v1.1
- Treatments:
 - Experimental: tiragolumab + atezolizumab + CE (induction phase; four 21-day cycles) followed by tiragolumab + atezolizumab (maintenance phase; 21-day cycles)
 - Control: placebo + atezolizumab + CE (induction phase; four 21-day cycles) followed by placebo + atezolizumab (maintenance phase; 21-day cycles)
- Intercurrent events:
 - Start of non-protocol anti-cancer therapy prior to a confirmed objective response is observed
 - Early discontinuation from study treatment for any reason prior to a confirmed objective response is observed
- Handling of intercurrent events: a treatment-policy with regards to the intercurrent events listed above will be applied
- Summary measure: difference in proportions of patients achieved confirmed objective response between treatments

An alternative estimand for confirmed ORR is defined similarly as above with the exception of the following:

- Population: patients with previously untreated extensive-stage small cell lung cancer

Confirmed ORR will be analyzed in patients with measurable disease at baseline and compared between treatment arms using Chi-square test. The 95% CI for the difference in confirmed ORRs between the two treatment arms will be computed using the Newcombe method. The 95% CI of the confirmed ORR will be calculated for each treatment arm using the Wilson score method.

5.4.2 Supportive Secondary Endpoint(s)

5.4.2.1 Duration of Response

Duration of response (DOR) will be assessed in the PAS and the FAS for patients who achieved a confirmed objective response, as determined by the investigator according to RECIST v1.1. DOR is defined as time from the date of the first occurrence of a confirmed objective response until the first date of progressive disease as determined by the investigator according to RECIST v1.1 or death from any cause, whichever occurs first. Patients who have not progressed and who have not died at the time of analysis will be censored at the time of the last tumor assessment date. DOR will be based on a non-randomized subset of patients (specifically, patients who achieve a confirmed objective response); therefore, hypothesis testing will not be performed for this endpoint. Comparisons between treatment arms will be made for descriptive purposes. Median DOR and corresponding 95% CIs will be estimated using Kaplan-Meier methodology for each treatment arm.

5.4.2.2 PFS and OS Rates at Selected Time Points

The PFS rates at 6 months and at 12 months are defined as the proportion of patients who have not experienced disease progression as determined by the investigator according to RECIST v1.1 or death from any cause at 6 months and 12 months after randomization. The PFS rates will be estimated using Kaplan-Meier methodology for each treatment arm, along with 95% CIs calculated using the standard error derived from Greenwood's formula. The 95% CI for the difference in PFS rates between the two treatment arms will be estimated using the normal approximation method, with standard errors computed using Greenwood's method.

Similar analyses will be performed for the OS rates at 1 and 2 years, defined as the proportion of patients who have not died from any cause at 12 months and 24 months after randomization.

5.4.2.3 Time to Confirmed Deterioration in Physical Functioning and Global Health Status

Patient-reported physical functioning (items 1-5) and global health status (GHS)/ quality of life (QoL) (items 29-30) as collected and measured by the European Organization for the Research and Treatment of Cancer (EORTC) Quality of Life Questionnaire Core 30

(QLQ-C30). A high score for the physical function subscale represents a high/healthy level of functioning and a high score for the GHS/QoL subscale represents a high health related quality of life. Both scales will be linearly transformed so that each score will range from 0 to 100. A score change of at least 10-point in GHS/QoL and functional subscale score is perceived by patients as clinically meaningful (Osoba et al. 1998).

The estimand for time to confirmed deterioration (TTCD) is defined as the follows:

- Population: patients with previously untreated extensive-stage small cell lung cancer without presence or history of brain metastases at baseline
- Variable: Time from randomization until the first confirmed clinically meaningful deterioration on physical functioning and GHS/QoL EORTC QLQ-C30 select scales; confirmed clinically meaningful deterioration is defined as a clinically meaningful decrease from baseline that must be held for at least two consecutive assessments or an initial clinically meaningful decrease from baseline followed by death from any cause within 3 weeks.
- Treatments:
 - Experimental: tiragolumab + atezolizumab + CE (induction phase; four 21-day cycles) followed by tiragolumab + atezolizumab (maintenance phase; 21-day cycles)
 - Control: placebo + atezolizumab + CE (induction phase; four 21-day cycles) followed by placebo + atezolizumab (maintenance phase; 21-day cycles)
- Intercurrent events:
 - Start of NPT prior to a confirmed clinical meaningful deterioration
 - Early discontinuation from study treatment for any reason prior to a confirmed clinical meaningful deterioration
 - Death that occurs before patients report any clinically meaningful deterioration
- Handling of intercurrent events: A treatment policy strategy with regards to the start of NPT and early discontinuation; and while-on-treatment/while-alive strategy for death will be applied for the TTCD analysis.
- Summary measure: Hazard Ratio for TTCD

An alternative estimand for TTCD is defined similarly as above with the exception of the following:

- Population: patients with previously untreated extensive-stage small cell lung cancer

For patients who discontinue study treatment for radiographic disease progression per RECIST v1.1 and enter the survival follow-up, the questionnaires will be completed at 3 months (± 30 days) and 6 months (± 30 days) following the visit in which progressive disease was confirmed. Patients who have not experienced a confirmed clinically meaningful deterioration by the clinical cutoff date will be censored at the last time when they completed an assessment. Patients with no baseline or post-baseline assessment will be censored at the date of randomization. According to the while on treatment/while-

alive strategy, patients who died before reporting any clinical meaningful deterioration will be censored at the last time when they completed an assessment. TTCD will be analyzed using the same methods as for the co-primary endpoint of PFS.

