6.4.1 Co-Primary Efficacy Endpoints

The co-primary efficacy endpoints are PFS (as assessed by the investigator according to RECIST v1.1) and OS in the PAS.

PFS is defined as the time between the date of randomization and the date of first documented disease progression (as assessed by investigators according to RECIST v1.1) or death, whichever occurs first. Patients who have not experienced disease progression and have not died by the time of analysis will be censored at the time of the last tumor assessment. Patients with no post-baseline tumor assessment will be censored at the date of randomization.

OS is defined as the time between the date of randomization and death from any cause.

Data for patients who are not reported as having died by the date of analysis will be censored at the date when they were last known to be alive. Data for patients who do not have post-baseline information will be censored at the date of randomization.

PFS and OS will be compared between treatment arms with use of the unstratified log-rank test. The HR for PFS and OS will be estimated using both unstratified and stratified Cox proportional hazards model. The 95% CI for the HR will be provided.

[REDACTED]

The investigator-assessed PFS rates at 6 months and at 1 year and OS rates at 1 year, 18 months, and 2 years after randomization will be estimated using Kaplan-Meier methodology for each treatment arm, along with 95% CIs calculated using the standard error derived from Greenwood's formula. The 95% CI for the difference in PFS rates and OS rates between the two treatment arms will be estimated using the normal approximation method.

The timing of the final PFS analysis is described in Section 6.1.1 and the analysis timing for OS is described in Section 6.1.2.

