6.4.2.4 Patient-Reported Outcomes

TTCD in the PAS and the FAS for physical functioning and GHS using the EORTC QLQ-C30 is defined as the time from the date of randomization until the first confirmed clinically meaningful deterioration. Confirmed clinically meaningful deterioration for GHS and physical functioning is defined as a clinically meaningful decrease from baseline in GHS or physical functioning scale score that must be held for at least two consecutive assessments or an initial clinically meaningful decrease above baseline followed by death. A score change of ≥ 10 -point is considered to be clinically meaningful by patients for lung cancer-related symptoms, GHS and physical functioning subscale score (Osaba et al. 1998).

For TTCD, data for patients will be censored at the last time when they completed an assessment if they have not experienced a confirmed clinically meaningful deterioration event at the CCOD. If no baseline or post-baseline assessment is performed, patients will be censored at the randomization date. TTCD using the EORTC scale will be analyzed using the same methods as for PFS. Further details regarding the TTCD analyses for the EORTC measures will be described in the SAP.

Summary statistics (mean, SD, median, 25th and 75th percentiles, and range) and the mean change from baseline of linear-transformed scores will be reported for all of the items and subscales of the EORTC QLQ-C30 and EORTC IL46 (an item for troubled by side effects) questionnaires at each timepoint, the end of treatment, at the time of progression (per RECIST criteria), and at the time of clinical progression (if different from time to progression). In addition, mean scores for GHS, physical functioning, and selected symptom scales will be presented for the induction phase and the maintenance phase.

PRO-CTCAE data will be analyzed by treatment arm, the number (percentage) of patients reporting symptom by "frequency," "severity," "interference," and "presence" at each assessment. In addition, the frequency of symptoms will be cross tabulated with the severity of the symptom to explore the impact of the symptom when it occurred.

A summary table of the percentage of patients reporting severity of a symptom as 'severe' or 'very severe' over the course of the study by treatment arm will also be provided. Finally, a longitudinal analysis of change may be employed to understand how symptoms may have changed over the course of treatment.

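### Any Kaplan-Meier curve, rate or median for TTCD would overstate the share who deteriorate while alive, because death is labelled while-alive but handled by censoring; the hazard ratio stands as cause-specific

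*SAP*

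**What the plan says.** SAP 5.4.2.3, and the matching row of SAP Table 2, list death before any reported deterioration as an intercurrent event and state that a "while-on-treatment/while-alive strategy for death will be applied for the TTCD analysis". The declared summary measure is the hazard ratio.

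The same section puts the strategy into practice by censoring: "patients who died before reporting any clinical meaningful deterioration will be censored at the last time when they completed an assessment". The only deaths that count as TTCD events are those that complete an unconfirmed drop, namely "an initial clinically meaningful decrease from baseline followed by death from any cause within 3 weeks".

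For the method, the SAP says "TTCD will be analyzed using the same methods as for the co-primary endpoint of PFS". Protocol 6.4.2.4 agrees: "TTCD using the EORTC scale will be analyzed using the same methods as for PFS".

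The text under SAP 5.3.2, where the main PFS analysis would be set out, is not visible. The PFS methods that can be read elsewhere are:
- Protocol 6.4.1: "PFS and OS will be compared between treatment arms with use of the unstratified log-rank test", with hazard ratios from Cox models.
- SAP 5.4.2.2: "The PFS rates will be estimated using Kaplan-Meier methodology for each treatment arm".
- SAP 5.3.5.1: "Kaplan-Meier estimates of median PFS and OS will be provided separately for each level of the subgroups".

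No cumulative-incidence or other competing-risk analysis of TTCD appears in the visible text.

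**The concern.** A while-alive strategy asks what happened to the patient up to death. A patient who dies without deteriorating can never deteriorate, so that death is a competing event. The PFS methods raise no such problem for PFS, because death is itself a PFS event. Carried over to TTCD, where most deaths are not events, Kaplan-Meier in effect gives the dead patients the later deterioration experience of those still being followed. The resulting curve is not the proportion who deteriorate while alive.

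The stake is descriptive. The trial does no formal testing (Protocol 6, SAP 2), so a curve or median read as a while-alive result is what a reader would take away. In extensive-stage small cell lung cancer deaths are frequent enough for the gap to be visible.

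**Working it through.** The documents state no event count, median or rate for TTCD, and the trial's own PFS and OS planning figures are redacted. There is no plan figure to reproduce.

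**Direction.** At each event time u, one minus Kaplan-Meier grows by S_T(u-) × dΛ_T(u). Here Λ_T is the cause-specific cumulative hazard of deterioration and S_T is the Kaplan-Meier estimate with deaths censored. The Aalen-Johansen cumulative incidence grows by S_T(u-) × S_D(u-) × dΛ_T(u), where S_D is the corresponding factor for death without deterioration. Since S_D ≤ 1, one minus Kaplan-Meier is never smaller, and it is larger as soon as one such death precedes a later deterioration. This needs no assumption about rates or independence.

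**Size, constant hazards.**
- λ_T = ln2/m, with net TTCD median m assumed to be 6, 12 or 24 months.
- λ_D = f × ln2/12.3 per month, with f assumed to be 25%, 50% or 100%. The 12.3 months is the median OS that Protocol 1.2 cites for atezolizumab plus CE. f = 100% means that patients without a drop die at the overall rate; smaller f means that deaths concentrate after deterioration.
- 1-KM(t) = 1 - exp(-λ_T t)
- CIF(t) = λ_T/(λ_T + λ_D) × [1 - exp(-(λ_T + λ_D) t)]

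Worked case, m = 12 and f = 50%: λ_T = 0.0578, λ_D = 0.0282, sum 0.0859.
- At 12 months 1-KM = 50.0%, and CIF = 0.672 × (1 - 0.357) = 43.2%.
- At 24 months the figures are 75.0% and 58.7%.

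All nine cases, in percent (gaps from unrounded values):

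| m | f | 12 mo 1-KM | CIF | gap | 24 mo 1-KM | CIF | gap | time CIF reaches 50% (months) |
|---|---|---|---|---|---|---|---|---|
| 6 | 25 | 75.0 | 70.3 | 4.7 | 93.8 | 85.2 | 8.6 | 6.4 |
| 6 | 50 | 75.0 | 66.1 | 8.9 | 93.8 | 77.8 | 15.9 | 6.8 |
| 6 | 100 | 75.0 | 58.7 | 16.3 | 93.8 | 66.1 | 27.6 | 7.9 |
| 12 | 25 | 50.0 | 46.4 | 3.6 | 75.0 | 66.1 | 8.9 | 13.5 |
| 12 | 50 | 50.0 | 43.2 | 6.8 | 75.0 | 58.7 | 16.3 | 15.9 |
| 12 | 100 | 50.0 | 37.7 | 12.3 | 75.0 | 47.3 | 27.7 | 38.6 |
| 24 | 25 | 29.3 | 27.1 | 2.2 | 50.0 | 43.2 | 6.8 | 31.7 |
| 24 | 50 | 29.3 | 25.1 | 4.2 | 50.0 | 37.7 | 12.3 | 77.2 |
| 24 | 100 | 29.3 | 21.7 | 7.6 | 50.0 | 29.5 | 20.5 | never |

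The Kaplan-Meier median equals m in every row.

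**Visit-based check.** A simulation used roughly the planned questionnaire schedule, confirmation at two assessments or death within 3 weeks of a drop, and censoring at the last form. With m of 6 or 12, f of 50% or 100%, and shared frailty variance 0, 0.5 or 1, it gave 12-month gaps of about 4 to 17 points.

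**Between arms, curves.** Take m = 12, f = 100%, no effect on the deterioration hazard, and a death hazard ratio of 0.7. Kaplan-Meier shows 75.0% in both arms at 24 months. The cumulative incidences are 53.7% with tiragolumab and 47.3% with control, because more patients live long enough to deteriorate.

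**Between arms, hazard ratio.** A simulation of 200,000 patients per arm assumed medians of 10 months to deterioration and 14 months to death without it, follow-up of 18 to 31 months, no deterioration effect and a death hazard ratio of 0.7. The TTCD hazard ratio was 0.987, 1.032 and 1.041 for frailty variance 0, 0.5 and 1.

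**The case against.** The strongest reply is that the estimand's declared summary measure is the hazard ratio. A Cox model that censors deaths estimates the cause-specific hazard ratio among patients still alive and free of deterioration, which is a legitimate while-alive quantity. This stands. A reader might infer that the TTCD hazard ratio is invalid; the documents do not support that.

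Second, no TTCD curve or median is named in the visible text. This also stands as a limit. Kaplan-Meier output is an inference from the reference to the PFS methods, well supported by the methods that can be read.

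Third, a reader might infer that the arm with more early deaths will look better on quality of life. That is not supported. In the simulation the sign changes with the assumed frailty (0.987 against 1.032 and 1.041), and frailty cannot be verified from these data. The shift is also small beside sampling error: with an assumed 25 events per arm, the 95% confidence factor is exp(1.96 × √(1/25 + 1/25)) = 1.74 either way.

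Fourth, a plain competing-risk analysis has its own weakness. After progression, questionnaires are due only at 3 and 6 months (Protocol 4.5.9.1, SAP 5.4.2.3). A death well after the last form leaves deterioration status unknown, and counting every such death as free of deterioration would bias the cumulative incidence downward. This stands and shapes the fix.

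**Conclusion.** The point holds for Kaplan-Meier output and not for the hazard ratio. SAP 5.4.2.3 attaches a while-alive label to a censoring rule, so any TTCD curve, rate or median produced by the PFS methods overstates the recorded proportion who deteriorate while alive. The direction is algebraic. The size is illustrative: about 2 to 16 points at 12 months and 7 to 28 points at 24 months over the assumed ranges.

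It would also be too strong to say that the curves describe a world in which nobody dies. That is exact only if death and deterioration are independent; with shared frailty, Kaplan-Meier matches neither that target nor the while-alive one.

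Severity is minor. SAP 5.4.2 classes TTCD as a supportive secondary endpoint, nothing is formally tested, and the consequence is for interpretation rather than type I error.

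**What to change.** In SAP 5.4.2.3 and the TTCD row of Table 2:

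1. Label the Cox hazard ratio as cause-specific.
2. Add the Aalen-Johansen cumulative incidence of confirmed deterioration by arm at 6 and 12 months, with the difference and 95% CI. Treat death without prior deterioration as a competing event only if it falls within a pre-stated window of the last completed form, for example two scheduled assessment intervals; otherwise censor at the last form. Add one sensitivity analysis that counts all such deaths.
3. Add one supplementary analysis of confirmed deterioration or death, using the same window.
4. If Kaplan-Meier curves or medians are kept, label them as censoring deaths and not as the while-alive estimate. Removing them altogether is a matter of preference.

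The primary-analysis cutoff is given as 31 August 2023 (Protocol 4.5.6). If results are already unblinded, report these as added analyses.

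The cost is SAP wording and standard software output, with no new data. The downside is slightly more output, and a cumulative incidence that is less directly comparable with earlier studies that censored deaths.

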5.5 EXPLORATORY ENDPOINTS ANALYSIS

5.5.1 Patient Reported Outcomes

[REDACTED]

[REDACTED]

[REDACTED]

5.5.2 Biomarker Analyses

[REDACTED]

5.6 SAFETY ANALYSES

Unless specified otherwise, safety analyses described below will be conducted for the safety evaluable set (see Section 5.4), with participants grouped according to whether any tiragolumab was received.

5.6.1 Extent of Exposure

Study drug exposure, including treatment duration, dosage, and dose intensity, will be summarized by treatment arm and for each study drug with descriptive statistics.

5.6.2 Adverse Events

Verbatim description of AEs will be mapped to the Medical Dictionary for Regulatory Activities (MedDRA) thesaurus terms. Severity for all adverse events will be graded by the investigator according to the National Cancer Institute Common Terminology Criteria for Adverse Events (NCI CTCAE) v5.0, and severity for cytokine-release syndrome (CRS) will also be graded by the investigator according to the American Society for Transplantation and Cellular Therapy (ASTCT) consensus grading scale.

All treatment-emergent adverse events will be summarized by treatment arm and NCI CTCAE grade. CRS will also be summarized by treatment arm and the ASTCT consensus grade. In addition, common adverse events, treatment-related AEs, serious adverse events (SAEs), adverse events leading to study treatment discontinuation or interruption, Grade 3-4 AEs, and fatal AE (Grade 5) will be summarized accordingly. For the purpose of analyses, adverse events of special interest (AESI) are identified by a set of comprehensive definitions using standardized MedDRA queries (SMQs), High-Level Terms (HLTs) and Sponsor-defined adverse event grouped terms (AEGTs) from the AE clinical database by medical concept. The AESI will be summarized by treatment arm and CTCAE grade.

Multiple occurrence of the same event will be counted once at the maximum severity.

For the safety analyses, “treatment-emergent” is defined as adverse events occurring on or after the first dose of study drug treatment or pre-existing condition that worsened on or after the first dose of the study treatment up to the data cutoff date.

Key adverse events that occurred during the induction and maintenance therapy phases may also be summarized separately.

Listings of adverse events will include all treatment emergent adverse events up to the data cutoff date.

Deaths during the study treatment period and those reported during the follow-up period after treatment completion or discontinuation and causes of death will be summarized by treatment arm.

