As of the primary *clinical cutoff date (CCOD)* of 30 June 2019, a total of 135 patients with a PD-L1 TPS $\geq 1\%$ (22C3) by local analysis were included in the intent-to-treat (ITT) population and were randomly assigned to tiragolumab plus atezolizumab ($n=67$) or placebo plus atezolizumab ($n=68$). The three stratification factors were well balanced between treatment groups. Of the enrolled patients, 43% had a TPS $\geq 50\%$ versus 57% of patients with a TPS 1%–49%; 59.3% had non-squamous histology versus 40.7% of patients who had squamous histology; and 10.4% were never-smokers versus 89.6% of patients who had smoked.

Demographics were generally well balanced between treatment groups as well, with a median age of 68 years in both the tiragolumab plus atezolizumab and placebo plus atezolizumab groups. There were more females (41.8% vs. 29.4%) and more White patients (62.7% vs. 58.8%) in the tiragolumab plus atezolizumab group compared with the placebo plus atezolizumab group.

As of the primary *CCOD* of 30 June 2019, the confirmed objective response rate (ORR) in the ITT population was higher in the tiragolumab plus atezolizumab arm (31.3%) than in the placebo plus atezolizumab arm (16.2%). Investigator-assessed PFS was also improved with a stratified HR of 0.57 (95% CI: 0.37, 0.90) with a median PFS not estimable and 3.9 months in the tiragolumab plus atezolizumab arm compared to the placebo plus atezolizumab arm, respectively. Responses to tiragolumab plus atezolizumab arm were observed in patients with both squamous and non-squamous histology. In the ITT population, 47.8% of patients in the tiragolumab plus atezolizumab group versus 27.9% of patients in the placebo plus atezolizumab group were still receiving study treatment. In the TPS $\geq 50\%$ population, 65.5% of patients in the tiragolumab plus atezolizumab group versus 24.1% of patients in the placebo plus atezolizumab group were still receiving study treatment.

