5.3.1 Adverse Event Reporting Period

Investigators will seek information on adverse events at each patient contact. All adverse events, whether reported by the patient or noted by study personnel, will be recorded in the patient's medical record and on the Adverse Event eCRF.

After informed consent has been obtained, but prior to initiation of study treatment, only serious adverse events caused by a protocol-mandated intervention (e.g., invasive procedures such as biopsies, discontinuation of medications) should be reported (see Section 5.4.2 for instructions for reporting serious adverse events).

After initiation of study treatment, all adverse events will be reported until █ days after the final dose of study treatment or until initiation of new systemic anti-cancer therapy, whichever occurs first, and serious adverse events will continue to be reported until █ days after the final dose of study treatment or until initiation of new systemic anti-cancer therapy, whichever occurs first. In addition, adverse events of special interest will continue to be reported until █ days after the final dose of study treatment, regardless of initiation of new systemic anti-cancer therapy.

Instructions for reporting adverse events that occur after the adverse event reporting period are provided in Section 5.6.

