1.2 STUDY DESIGN

[figure not shown]
This is a Phase III, randomized, double-blind, placebo-controlled multicenter study in China designed to evaluate the safety and efficacy of tiragolumab plus atezolizumab and CE compared with placebo plus atezolizumab and CE in patients with chemotherapy-naïve ES-SCLC.

Eligible patients are stratified by Eastern Cooperative Oncology Group (ECOG) Performance Status (0 vs. 1) and lactate dehydrogenase (LDH) (\leq upper limit of normal [ULN] vs. $>$ ULN), and will be randomized 1:1 to receive one of the following treatment regimens:

- Arm A: tiragolumab + atezolizumab + CE (induction phase; four 21-day cycles) followed by tiragolumab + atezolizumab (maintenance phase; 21-day cycles)
- Arm B: placebo + atezolizumab + CE (induction phase; four 21-day cycles) followed by placebo + atezolizumab (maintenance phase; 21-day cycles)

The study schema is shown in [Figure 1](#).

Figure 1 Study Schema

CE=carboplatin and etoposide; ECOG PS=Eastern Cooperative Oncology Group performance scale; ES-SCLC= extensive-stage small cell lung cancer ; FAS=full analysis set; LDH=lactate dehydrogenase; n=number of patients; PAS= primary analysis set; RECIST=Response Evaluation Criteria in Solid Tumors; ULN=upper limit of normal.

Following the induction phase, patients will continue maintenance therapy with either tiragolumab plus atezolizumab (Arm A) or placebo plus atezolizumab (Arm B).

Treatment will be continued until radiographic disease progression according to Response Evaluation Criteria in Solid Tumors (RECIST) version 1.1, or as long as patients are experiencing clinical benefit, as assessed by the investigator, in the absence of unacceptable toxicity or symptomatic deterioration attributed to disease progression after an integrated assessment of radiographic data, biopsy results (if available), and clinical status. Patients who meet the criteria for disease progression per Response Evaluation Criteria in Solid Tumors (RECIST) v1.1 will be permitted to continue study treatment (atezolizumab plus tiragolumab or atezolizumab plus placebo) if they meet all of the criteria specified in study protocol (see Protocol, Section 3.1.2) and provide written consent.

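### Adverse events are compared as crude patient incidence over a window that follows time on treatment, so unequal exposure would shift the comparison even at equal event rates

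*SAP*

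**What the plan says.** The safety objective is comparative: incidence and severity of adverse events, tiragolumab arm against placebo arm (Protocol 2.2; SAP Table 1). SAP 5.6.2 implements it as follows: "All treatment-emergent adverse events will be summarized by treatment arm and NCI CTCAE grade", and "Multiple occurrence of the same event will be counted once at the maximum severity". Protocol 6.5 takes the same approach.

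Three further provisions set how long each patient can contribute an event.

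- Treatment has no fixed length. SAP 1.2: "Treatment will be continued until radiographic disease progression" per RECIST v1.1, or for as long as there is clinical benefit.
- Collection is tied to the last dose. Protocol 5.3.1 ends it a redacted number of "days after the final dose of study treatment or until initiation of new systemic anti-cancer therapy, whichever occurs first". Adverse events and serious adverse events have separately stated windows. Events of special interest are also anchored to the final dose, but there new therapy does not close the window.
- The treatment-emergent definition imposes no common window. It takes in new events from the first dose and any "pre-existing condition that worsened on or after the first dose of the study treatment up to the data cutoff date".

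Two provisions bear on the problem without solving it. SAP 5.6.1: "Study drug exposure, including treatment duration, dosage, and dose intensity, will be summarized by treatment arm". SAP 5.6.2 also allows, but does not require, key events to be shown separately for induction and maintenance. The unredacted text of both documents plans no exposure-adjusted rate, time-to-first-event analysis, cumulative incidence or fixed-window comparison of adverse events.

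**The concern.** A patient observed for two months and one observed for twenty months each count as one in the denominator. If one arm stays on treatment longer, its patients have more time in which to have a first event, and the crude percentage rises with no change in the event rate. The safety comparison then partly reflects the difference in treatment duration.

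A duration difference is plausible. In the randomized Phase II study in non-small cell lung cancer described in Protocol 1.4.1.3, "47.8% of patients in the tiragolumab plus atezolizumab group versus 27.9% of patients in the placebo plus atezolizumab group were still receiving study treatment" at the cutoff.

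Two uses of the tables are exposed. Protocol 1.5 expects toxicity comparable with standard of care, and crude tables cannot examine that cleanly when exposure differs. Protocol 5.7 has imbalances unfavourable to the test product reported to health authorities. Longer treatment alone could contribute to such an imbalance, and shorter treatment could mask a real one.

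**Working it through.** The plan gives no figure for the adverse event comparison, so there is none to reproduce. The check asks how far crude incidence moves when the true event rate is the same in both arms.

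**Inputs**

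- Control time on treatment: exponential with median 5.2 months. This is the median PFS of atezolizumab plus chemotherapy in Protocol 1.2, used as a proxy (assumption). The control stopping rate is μ = ln 2 / 5.2 = 0.1333 per month.
- Experimental stopping rate: HR × μ. The trial's target HR is redacted, so a range is used: 0.90 (assumed), 0.77 (the PFS HR in Protocol 1.2) and 0.57 (the Phase II PFS HR in Protocol 1.4.1.3).
- Post-dose tail w: redacted; 0, 1 and 3 months assumed.
- First-event hazard λ: the same constant in both arms, 0.02 to 0.20 per month (assumed).
- About 128 patients randomized 1:1, so about 64 per arm.

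**Formulas**

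- Crude incidence: P = 1 − exp(−λw) × μ/(μ+λ)
- Mean time at risk to first event: R = (1 − exp(−λw))/λ + exp(−λw)/(μ+λ)
- Exposure-adjusted rate: P/R

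**One case in full: λ = 0.10, w = 1, HR = 0.77**

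- Control: P = 1 − 0.9048 × 0.1333/0.2333 = 48.3%
- Experimental, stopping rate 0.77 × 0.1333 = 0.1026: P = 1 − 0.9048 × 0.1026/0.2026 = 54.2%
- Artefact: 5.9 points, about 31 against 35 of 64 patients. Mean window: 8.5 against 10.7 months.
- Control R = 0.9516 + 0.9048/0.2333 = 4.83 months, and 0.483/4.83 = 0.10 per month.
- Experimental R = 0.9516 + 0.9048/0.2026 = 5.42 months, and 0.542/5.42 = 0.10 per month.
- Both arms have 120 events per 100 patient-years, so the adjusted rates agree.

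**Across the range**

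| HR for time on treatment | λ = 0.05, w = 1 | λ = 0.10, w = 1 | Excess over λ 0.02–0.20, w 0–3 |
|---|---|---|---|
| 1.00 | 30.8% vs 30.8% | 48.3% vs 48.3% | 0 |
| 0.90 | 30.8% vs 32.9% | 48.3% vs 50.7% | 1.2–2.6 points |
| 0.77 | 30.8% vs 36.0% | 48.3% vs 54.2% | 3.1–6.5 points |
| 0.57 | 30.8% vs 42.6% | 48.3% vs 60.9% | 6.8–14.0 points |

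**Induction phase only.** For on-treatment events in the four 21-day cycles (12 weeks, t = 2.76 months), P = λ/(λ+μ) × (1 − exp(−(λ+μ)t)). With λ from 0.05 to 0.20 the excess is 0.2 to 0.6 points at HR 0.90, 0.4 to 1.3 at HR 0.77 and 0.8 to 2.5 at HR 0.57. The artefact therefore lies mainly in events that continue to accrue during maintenance.

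**The case against.** A reader might infer that the planned tables will overstate tiragolumab's toxicity, and that the Phase II study already shows it. The documents do not support that. At the same cutoff as the exposure figures, Protocol 1.4.1.3 reports crude Grade ≥ 3 events of 41.8% vs 44.1%, serious events of 34.3% vs 35.3% and withdrawals due to adverse events of 7.5% vs 10.3%, none higher on tiragolumab. Treatment-related events (80.6% vs 72.1%) and immune-mediated events (65.7% vs 47.1%) were higher, but crude figures cannot say how much of that is exposure. The study was also in a different disease and without chemotherapy.

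Other points on that side have weight.

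- Both arms share the same four planned cycles of chemotherapy, and events in that period are barely affected.
- PFS is an imperfect proxy for time on treatment, because treatment beyond progression and stopping for toxicity are both possible.
- Safety is descriptive in a study not powered for efficacy, and no decision rule uses the tables. With 64 per arm, the 95% half-width for 48.3% vs 54.2% is 1.96 × √(0.483 × 0.517/64 + 0.542 × 0.458/64) = 17 points, well above the 5.9-point artefact.
- Crude incidence is a legitimate quantity: the risk experienced on the regimen as given. Exposure is tabulated, and discontinuations, interruptions and deaths are shown separately.

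These points limit size and priority. They do not remove the mechanism. Sampling error is random, whereas the artefact pushes all accruing categories in the same direction. The exposure table lets a reader see an imbalance but not correct for it. The phase split is optional, and patients in maintenance still have unequal time at risk.

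**Conclusion.** The point holds as a conditional one. The planned comparison is a crude incidence; the SAP does not print the word percentages for adverse events, but this follows from the incidence endpoint, the count-once rule and the absence of a time denominator. The collection window follows time on treatment. If time on treatment differs, crude incidence differs at identical rates: about 1 to 3 points at HR 0.90, 3 to 6.5 at 0.77 and 7 to 14 at 0.57, under a constant hazard, a 5.2-month control median and a 0 to 3 month tail. It is zero at equal exposure and about 0.2 to 2.5 points for induction-phase events. If the tiragolumab arm stops earlier, the sign reverses and its event rate is understated. The redacted target HR and tail leave the true size and direction open. This is a matter of interpretation, with no type I error involved, and it calls for a modest addition to the SAP.

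**What to change.** In SAP 5.6.2, keep the crude tables and make these changes.

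1. Add exposure-adjusted incidence rates per 100 patient-years at risk, with the rate ratio and 95% CI, for all adverse events, Grade 3–5 events, serious events, events of special interest and events leading to discontinuation. Count time from first dose to first event or, without an event, to the end of the reporting window for that category. For events of special interest, Protocol 5.3.1 and 5.4.2.2 keep the window open after new therapy while the adverse event footnote in Appendix 1 closes it; reconcile these before programming.
2. For the induction/maintenance summary, change *may* to *will*.
3. Optionally, add cumulative incidence of time to first event for key categories, with death as a competing event and other window closures censored, stating that this censoring may be informative. Late timepoints will be thin: under the 5.2-month median, 0.5^(12/5.2) = 20% of controls, about 13 of 64, remain on treatment at 12 months.
4. State that the between-arm safety comparison is interpreted alongside these results and does not rest on them alone.

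The cost is SAP wording and a few extra tables. The inputs should already be available, since treatment duration, new anti-cancer therapy and survival are collected. The main limitation is that rates per patient-year assume a roughly constant hazard. They can mislead for events concentrated in early cycles, which the phase split partly addresses.
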